# 7.3.4. Probability of Experiencing a BILAG A Flare

Endpoint: The British Isles Lupus Assessment Group (BILAG) 2004 (2007 Revision) instrument will be completed at baseline and every follow-up visit, including any Flare or Endpoint visits, during the course of the 60 week study period for all subjects. Data for this assessment will be collected on the Modified BILAG: Constitutional, Modified BILAG: Musculoskeletal, Modified BILAG: Cardiorespiratory, Modified BILAG: Gastrointestinal, Modified BILAG: Ophthalmic, Modified BILAG: Renal, and Modified BILAG: Hematological CRF pages.

The rules for scoring the BILAG 2004 are in Appendix 14.4 *BILAG 2004 Index Scoring*. In each of the nine body system categories (constitutional, mucocutaneous, neuropsychiatric, musculoskeletal, cardiorespiratory, gastrointestinal, ophthalmic, renal, and hematological) subjects are assessed on a variety of disease activity criteria. Each category is then scored as an A, B, C, or D/E, where A indicates most severe disease activity and D/E indicates inactive/no disease activity. For this study the following additional scoring rules are applied:

 According to the scoring algorithm, D means "Inactive disease but previously affected", and E means "System never involved". Since we may not know whether the subject has ever experienced involvement in a particular system prior to starting the study, we will not attempt to distinguish between D and E. Subjects will be assigned the score "D/E" if they did not meet the criteria for A, B, or C at the particular visit.

Version: 1.0 Page 22 of 48

- 2. In the Renal category, some of the scoring rules require looking at previous measurements to assess change (e.g., 24 hour protein > 1g that has not decreased (improved) by >=25%). At Screening the BILAG is not collected as it is not required for eligibility purposes. As such, no previous BILAG assessment is available to refer to for applying such rules at the Day 0 visit and therefore subjects will not have a renal score assigned at Day 0.
- 3. In the Renal category, the original instrument includes an evaluation of proteinuria based on the protein:creatinine ratio derived from a 24-hour urine. For this study, the protein:creatinine ratio will typically be derived from the spot urine assessment although a 24-hour urine may be used if the spot urine assessment is not available.

For each subject, a yes/no variable will be created to indicate whether a subject had at least one BILAG A flare, in any body system, by Week 60. Subjects who terminate early from the study prior to experiencing a BILAG A flare will be categorized as not experiencing a BILAG A flare by Week 60.

The probability of experiencing any BILAG A flare will be calculated for each study arm.

Additionally, for each subject, the total number of visits with BILAG A flare will be tabulated.

**Analysis**: Analyses analogous to those specified for the primary endpoint (effect estimates and 95% confidence intervals, risk difference, and summaries of increased risk (a) vs.% confidence the "true" risk is  $\leq a$ ) will be performed for the probability of experiencing a BILAG A flare by Week 60. See Section 7.2.2, *Primary Analysis of the Primary Endpoint*, for more details on the analyses. The total number of visits that a subject has with a BILAG A flare will be summarized by treatment group and overall. Summary tables for BILAG A scoring by body system will be provided.

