# 7.2.2. Primary Analysis of the Primary Endpoint

The planned analyses for this study are designed to maximize the information available for medical decision-making. The planned analyses are as follows:

Effect estimates and 95% confidence intervals for the risk of disease reactivation by Week 60 in each arm as well as the estimated risk difference (i.e. risk\_MMFwithdrawal - risk\_MMF maintenance) and 95% confidence intervals around the risk difference will be reported using the Kaplan-Meier product-limit estimator.

The observed risk estimates will be used to compute the "% Confidence that the true increase is  $\leq$  a" as a function of values for the "Acceptable increase in risk with withdrawal of MMF (a)". This information will be plotted with values for "Acceptable increase in risk with withdrawal of MMF (a)" on the x axis and estimates for "% Confidence that the true increase is  $\leq$  a" on the y axis. The study will generate a single curve based on the observed risk estimates for the two arms. Physicians with their patients could decide on an acceptable level of increased risk (a) then read from the plot the % confidence that this selected value of a would not be exceeded with withdrawal of MMF. Depending on the level of confidence, they may or may not decide to withdraw MMF.

Version: 1.0 Page 19 of 48

The motivation for the curve comes from the test of non-inferiority with the following hypotheses:

 $H_0$ : the increase in risk with withdrawal of MMF ( $\mathbf{T}$ )  $\geq \mathbf{a}$ , and  $H_A$ : the increase in risk with withdrawal of MMF ( $\mathbf{T}$ )  $< \mathbf{a}$ , where  $\mathbf{a}$  is some value for the acceptable increase in risk.

The  $H_0$  hypothesis would be rejected in favor of  $H_A$  if the upper (1- $\alpha$ ) % confident limit about the estimated risk difference (i.e. risk\_MMFwithdrawal - risk\_MMF maintenance) is less than  $\boldsymbol{a}$ . Then, we could conclude that  $\boldsymbol{T} < \boldsymbol{a}$  with (1- $\alpha$ )% confidence. Physicians and patients who are comfortable with both a risk increase of no more than  $\boldsymbol{a}$  and a confidence level of (1- $\alpha$ )% could conclude that withdrawal from MMF is "not unacceptably worse" than maintenance on MMF.

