# 7.3.2. Probability of Experiencing a SELENA-SLEDAI Flare

**Endpoint**: The SELENA-SLEDAI instrument will be completed at baseline and every follow-up visit, including any Flare or Endpoint visits, during the course of the 60 week study period for all subjects. The SELENA-SLEDAI assesses SLE disease activity and flares based on changes in the SLEDAI score, the Physician's Global Assessment (PGA), medication use (prednisone, NSAIDS, Plaquenil, major immunosuppressives), other disease activity criteria, and hospitalization due to SLE. See Section 7.2.1., *Computation of the Primary Endpoint*, for more information on scoring of the SELENA-SLEDAI flare assessment.

For each subject, a yes/no variable will be created to indicate whether a subject had at least one mild/moderate or severe SELENA-SLEDAI flare by Week 60 and separately whether the subject had at least one severe SELENA-SLEDAI flare by Week 60. Subjects who terminate early from the study prior to experiencing any SELENA-SLEDAI flare will be categorized as not experiencing any SELENA-SLEDAI flare by Week 60.

Additionally, for each subject, the total number of visits with mild/moderate or severe SELENA-SLEDAI flares will be tabulated, including categorizing number of flare visits for a subject into 0, 1, or >1 flare.

The probability of experiencing any SELENA-SLEDAI flare and the probability of experiencing any severe SELENA-SLEDAI flare by Week 60 will be calculated in aggregate and within subgroups defined by disease manifestation (renal disease/extra-renal disease) and by baseline MMF dosing group (<2000 mg per day / ≥ 2000 mg per day).

**Analysis**: Analyses analogous to those specified for the primary endpoint (effect estimates and 95% confidence intervals, risk difference, and summaries of increased risk ( $\alpha$ ) vs.% confidence the "true" risk is  $\leq \alpha$ ) will be performed for the probability of experiencing any SELENA-SLEDAl flare and any severe SELENA-SLEDAl flare by Week 60, including analyses within subgroups for disease manifestation and baseline MMF dose. See Section 7.2.2, *Primary Analysis of the Primary Endpoint*, for more details on the analyses.

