# 7.3.5. Subjects in the Renal Subgroup with BILAG Renal A Flares

**Endpoint**: The BILAG instrument will be completed at baseline and every follow-up visit during the course of the 60 week study period for all subjects. See Section 7.3.4, *Probability of Experiencing a BILAG A Flare*, for more information on the BILAG and its scoring. The renal disease subgroup includes subjects who presently have renal disease as well as those who have had renal manifestations in the past, as specified by the site at randomization.

For each subject in the renal subgroup, a yes/no variable will be created to indicate whether a subject had at least one BILAG A flare in the renal body system by Week 60. Subjects in the renal subgroup, who terminate early from the study prior to experiencing a BILAG A renal flare, will be categorized as not experiencing a BILAG A flare by Week 60.

The proportion of subjects in the renal subgroup with at least one BILAG A flare in the renal body system by Week 60 will be calculated for each study arm.

**Analysis**: Analyses analogous to those specified for the primary endpoint (effect estimates and 95% confidence intervals, risk difference, and summaries of increased risk ( $\alpha$ ) vs.% confidence the "true" risk is  $\leq \alpha$ ) will be performed for the probability of experiencing a BILAG A renal flare by Week 60 in the renal subgroup. See Section 7.2.2, *Primary Analysis of the Primary Endpoint*, for more details on the analyses.

Version: 1.0 Page 23 of 48

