# 7.3.6. Probability of Experiencing a BILAG A or B Flare

**Endpoint**: The BILAG instrument will be completed at baseline and every follow-up visit, including any Flare or Endpoint visits, during the course of the 60 week study period for all subjects. See Section 7.3.4, *Probability of Experiencing a BILAG A Flare*, for more details on the BILAG assessment.

For each subject, a yes/no variable will be created to indicate whether a subject had at least one BILAG A or B flare, in any body system, by Week 60. Subjects who terminate early from the study prior to experiencing a BILAG A or B flare will be categorized as not experiencing a BILAG A or B flare by Week 60.

The probability of experiencing any BILAG A or B flare will be calculated for each study arm by each body system and overall.

Additionally, for each subject, the total number of visits with a BILAG A or B flare will be tabulated by arm for each body system and overall.

**Analysis**: Analyses analogous to those specified for the primary endpoint (effect estimates and 95% confidence intervals, risk difference, and summaries of increased risk ( $\alpha$ ) vs.% confidence the "true" risk is  $\leq \alpha$ ) will be performed for the probability of experiencing a BILAG A flare by Week 60. See Section 7.2.2, *Primary Analysis of the Primary Endpoint*, for more details on the analyses. Summary tables for BILAG scoring by body system will be provided. The total number of visits that a subject has with a BILAG A or B flare will be summarized by treatment group and overall.

The study day of flare, type (A or B), body system, and number of flares for each subject will also be shown graphically over time by subject and treatment group.

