# 7.3.8. The Addition of Aggressive Adjunctive Therapy to MMF or Change in MMF Therapy to Cytotoxic Drug Due to Flare

**Endpoint**: Medications are assessed at each study visit throughout the duration of the study and are collected on the *Prior/Concomitant Medications* CRF page.

For both the maintenance and withdrawal arms, the addition of aggressive adjunctive therapy can include IV immunoglobulin or rituximab at any point during the subject's participation in the study. A change in therapy to cytotoxic drug due to flare can include drugs such as cyclophosphamide, etc. A blinded list of study medications will be reviewed to identify the addition of aggressive adjunctive therapy or cytotoxic drugs.

For each subject, a yes/no variable will be created to indicate whether a subject added aggressive adjunctive therapy to MMF or changed MMF therapy to cytotoxic drug due to flare by Week 60. Subjects off MMF in the withdrawal arm will be included in the endpoint if aggressive adjunctive therapy or cytotoxic drugs were added to treat a flare. Subjects who terminate early from the study prior to adding aggressive adjunctive therapy to MMF or changing MMF therapy to cytotoxic drug due to flare will be categorized as not meeting the endpoint.

The probability of adding aggressive adjunctive therapy to MMF or changing MMF therapy to cytotoxic drug due to flare will be calculated for each study arm.

**Analysis**: Analyses analogous to those specified for the primary endpoint (effect estimates and 95% confidence intervals, risk difference, and summaries of increased risk ( $\alpha$ ) vs.% confidence the "true" risk is  $\leq \alpha$ ) will be performed for adding aggressive adjunctive therapy to MMF or changing MMF therapy to cytotoxic drug due to flare by Week 60. See Section 7.2.2, *Primary Analysis of the Primary Endpoint*, for more details on the analyses. Additionally, type of new therapy will be summarized by treatment arm and overall.

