#### 12. CHANGES TO THE ANALYSES PLANNED IN THE PROTOCOL

[figure not shown]
- Section 7.2. Primary Endpoint. Statistical methods to obtain effect estimates and confidence intervals for the probability of observing clinically significant disease reactivation by 60 weeks have been changed from exact methods for complete data (proportions with Clopper Pearson intervals) to Kaplan-Meier predict-limit estimators to allow for censoring of subjects who terminated early without evidence of disease reactivation.
- 2. Section 7.3.3. Time to First SELENA-SLEDAI Flare: Time to first SELENA-SLEDAI flare has been changed from using withdrawal date to using Day 0 date. This allows us to calculate time to first SELENA-SLEDAI flare in both arms, since the Maintenance arm does not start withdrawal, and is consistent with the timing of the time to disease reactivation endpoint specified in Section 7.3.1.
- 3. Section 7.3.6. Probability of Experiencing a BILAG A or B Flare: This is a new endpoint was added to the SAP by the study team.
- 4. Section 11.1. Interim Analysis: The sample size re-estimation specified if ≤ 10% of the first 80 subjects experienced disease reactivation was not performed. We observed that after 60 weeks of post-randomization, 8 of the first 80 (10%) subjects experienced disease reactivation. Although the rate of disease reactivation was low, the team opted not to re-estimate the sample size. Rates of BILAG and SELENA-SLEDAI flares, which will also be important for evaluating the impact of MMF withdrawal, are higher than 10%. The larger sample size is necessary to improve precision for these important secondary endpoints and will strengthen the primary analysis.

Version: 1.0 Page 36 of 48

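### Five secondary flare and therapy endpoints count early leavers as non-events yet are sent to Kaplan-Meier; for the BILAG and therapy endpoints no event date or censoring rule settles which applies

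*SAP*

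**What the plan says.** **Coding of early leavers.** Five sections of the SAP define a yes/no variable and fix its value for subjects who leave before an event.

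- 7.3.2, any SELENA-SLEDAI flare: those who leave "prior to experiencing any SELENA-SLEDAI flare will be categorized as not experiencing any SELENA-SLEDAI flare by Week 60".
- 7.3.4, BILAG A flare: those who leave "prior to experiencing a BILAG A flare will be categorized as not experiencing a BILAG A flare by Week 60".
- 7.3.5, renal BILAG A flare: they "will be categorized as not experiencing a BILAG A flare by Week 60". The quantity to be calculated per arm is "The proportion of subjects in the renal subgroup with at least one BILAG A flare in the renal body system by Week 60".
- 7.3.6, BILAG A or B flare: they "will be categorized as not experiencing a BILAG A or B flare by Week 60".
- 7.3.8, adjunctive or cytotoxic therapy: those who leave before adding such therapy or "changing MMF therapy to cytotoxic drug due to flare will be categorized as not meeting the endpoint". This section does not add the Week 60 wording to the rule.

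**Analysis.** Each of the five asks for analyses analogous to the primary endpoint and cites 7.2.2, where the arm risks, the risk difference and their intervals "will be reported using the Kaplan-Meier product-limit estimator". SAP Section 12, item 1, says that this method replaced complete-data proportions for the primary endpoint "to allow for censoring of subjects who terminated early without evidence of disease reactivation". That item names Section 7.2 only.

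**Related text.** SAP 7.2.1 gives the primary endpoint a yes/no variable, an event date and censoring at the last visit. SAP 7.3.3 does the same for time to SELENA-SLEDAI flare. Protocol 8.5.5 sets a default of no imputation, with departures to be specified in the SAP.

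**The concern.** Take a subject who leaves at Week 16 without a BILAG A flare. Read literally, the coding rule makes that subject flare-free to Week 60. Under Kaplan-Meier the subject contributes 16 weeks and is then censored. The two instructions give different arm probabilities, and 7.3.4, 7.3.5, 7.3.6 and 7.3.8 contain no event date or censoring rule to show which one governs.

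If the crude proportion is reported, unobserved time counts as event-free time and both arm risks come out low. The risk difference, and the curve of confidence against acceptable increase, shift too if dropout differs between arms. For SELENA-SLEDAI flare, a crude figure under 7.3.2 would sit beside the Kaplan-Meier Week 60 figure under 7.3.3, so one report could carry two values for the same risk.

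These endpoints carry some weight. SAP Section 12, item 4, cites precision for the BILAG and SELENA-SLEDAI flare rates as a reason for not re-estimating the sample size. The early-termination sensitivity analysis in SAP 7.2.3 covers the primary endpoint only, so it would not reveal the discrepancy here.

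**Working it through.** **Plan figures.** The plan gives no dropout rate and no numerical assumption for these endpoints, so there is no figure of its own to reproduce on this point. Table 8.1 of the protocol concerns the primary endpoint. Its lead cell reproduces: SE = √[(0.05×0.95 + 0.10×0.90)/60] = 0.0479, and Φ(0.10/0.0479 − 1.036) = 85.4% against the stated 85%. Nothing below changes it.

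**Inputs.**
- 60 subjects per arm: protocol 8.1, 120 randomised 1:1.
- Dropout d by Week 60: not stated. Assumed 5% to 20% per arm, non-informative, with leaving times uniform over 60 weeks. SAP 7.2.1 says only that dropout is likely to occur as a trial lengthens.
- True Week 60 risk p: SAP Section 12 says only that the flare rates exceed 10%. Assumed 0.10 to 0.50, with constant hazard.

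**Formula.** With λ = −ln(1 − p) per 60 weeks, a leaver has had the event before leaving with probability m = 1 − p/λ. The expected crude proportion is

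q = (1 − d)p + d·m.

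For p = 0.40: λ = 0.5108 and m = 1 − 0.40/0.5108 = 0.2170. At d = 0.20, q = 0.80×0.40 + 0.20×0.2170 = 0.363.

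| True risk p | m | q, d = 5% | q, d = 10% | q, d = 20% |
|---|---|---|---|---|
| 0.10 | 0.0509 | 0.098 | 0.095 | 0.090 |
| 0.20 | 0.1037 | 0.195 | 0.190 | 0.181 |
| 0.30 | 0.1589 | 0.293 | 0.286 | 0.272 |
| 0.40 | 0.2170 | 0.391 | 0.382 | 0.363 |
| 0.50 | 0.2787 | 0.489 | 0.478 | 0.456 |

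The relative shortfall is d(1 − m/p). It approaches d/2 for small p, so it is at most about 2.5% at 5% dropout and 10% at 20% dropout. At p = 0.40 it is 2.3% to 9.2%.

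**Kaplan-Meier check.** In 5,000 simulated arms of 60 with 20% dropout, Kaplan-Meier averaged 0.399 for a true 0.40 and 0.200 for a true 0.20. The crude proportion averaged 0.363 and 0.181.

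**Risk difference.** True 0.40 (withdrawal) against 0.30 (maintenance), so the true increase is 0.100:

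| Dropout, maintenance / withdrawal | Crude risks, withdrawal − maintenance | Crude difference |
|---|---|---|
| 10% / 10% | 0.3817 − 0.2859 | 0.096 |
| 20% / 20% | 0.3634 − 0.2718 | 0.092 |
| 10% / 20% | 0.3634 − 0.2859 | 0.078 |
| 20% / 10% | 0.3817 − 0.2718 | 0.110 |

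Equal dropout shrinks the difference a little. Greater dropout in the withdrawal arm shrinks it more. In this example, greater dropout in the maintenance arm inflates it.

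**The case against.** The strongest reply is that the SAP uses the same phrasing for the primary endpoint. Section 7.2.1 categorises most early leavers as not having reactivated, then censors them at the last visit and takes the risk from Kaplan-Meier. On that pattern the yes/no variable is just the event indicator, and the five secondary sections inherit the rest through their reference to 7.2.2. Read that way, 7.3.2 and 7.3.3 agree and there is no bias. This reading is available, and it rules out saying that the SAP commits to the crude estimate. It does not make the text clear: 7.2.1 needed an explicit event date and censoring rule to work, and the BILAG and therapy sections have neither.

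A reader might also infer that only a crude proportion could be computed for these endpoints. The documents do not support that. BILAG is completed at every follow-up visit, 7.3.6 plots the study day of each flare, and medications are assessed at each visit.

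A reader might further infer that the error always makes withdrawal look safer. That does not follow either: the direction depends on which arm loses more subjects, and no document says which.

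Two more points stand. The design limits dropout: subjects who stop treatment for disease activity or toxicity are to continue visits (protocol 5.10.1 and 5.10.1.1), and those who withdraw are asked for a full final assessment (protocol 5.10.2.1 and 6.4.4.4). And the endpoints are exploratory (SAP 7.3).

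**Conclusion.** The concern holds as an unresolved choice between two estimators, one of which is biased. For the BILAG and adjunctive-therapy endpoints the text permits a crude proportion that understates each arm's Week 60 risk whenever early leavers remain at risk after leaving. For SELENA-SLEDAI flare, 7.3.3 supplies the censoring rule but 7.3.2 does not refer to it.

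The size is modest. At a true risk of 0.40 and 20% dropout the shortfall is 0.037, a little over half the simulated Kaplan-Meier standard deviation of 0.067 for an arm of 60; at 5% dropout it is 0.009. A true difference of 0.100 could be reported as 0.078 or 0.110, depending on which arm loses more subjects. All of this rests on assumed dropout and flare rates, constant hazards, uniform leaving times and non-informative dropout. The primary analysis and Table 8.1 are not affected. The wording should be corrected because the repair is cheap and the SAP itself calls the flare endpoints important.

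**What to change.** In SAP 7.3.2, 7.3.4, 7.3.5, 7.3.6 and 7.3.8, state that:

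1. the yes/no variable is only the event indicator;
2. time runs from Day 0 to the first event, and subjects without the event are censored at the last visit with that assessment;
3. the Week 60 probability, risk difference and confidence curve are Kaplan-Meier estimates as in 7.2.1 and 7.2.2.

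Keep the crude count or proportion as descriptive or sensitivity output. This includes the proportion in 7.3.5, which is how the protocol names that endpoint.

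The cost is a few sentences and the use of visit dates already collected. Intervals widen slightly: for one arm at a true 0.40 with 20% dropout, the standard deviation is 0.067 for Kaplan-Meier against √(0.363×0.637/60) = 0.062 for the crude proportion. Kaplan-Meier also relies on non-informative censoring, which is a further reason to show the crude figures alongside it.

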# 7.3.5. Subjects in the Renal Subgroup with BILAG Renal A Flares

**Endpoint**: The BILAG instrument will be completed at baseline and every follow-up visit during the course of the 60 week study period for all subjects. See Section 7.3.4, *Probability of Experiencing a BILAG A Flare*, for more information on the BILAG and its scoring. The renal disease subgroup includes subjects who presently have renal disease as well as those who have had renal manifestations in the past, as specified by the site at randomization.

For each subject in the renal subgroup, a yes/no variable will be created to indicate whether a subject had at least one BILAG A flare in the renal body system by Week 60. Subjects in the renal subgroup, who terminate early from the study prior to experiencing a BILAG A renal flare, will be categorized as not experiencing a BILAG A flare by Week 60.

The proportion of subjects in the renal subgroup with at least one BILAG A flare in the renal body system by Week 60 will be calculated for each study arm.

**Analysis**: Analyses analogous to those specified for the primary endpoint (effect estimates and 95% confidence intervals, risk difference, and summaries of increased risk ( $\alpha$ ) vs.% confidence the "true" risk is  $\leq \alpha$ ) will be performed for the probability of experiencing a BILAG A renal flare by Week 60 in the renal subgroup. See Section 7.2.2, *Primary Analysis of the Primary Endpoint*, for more details on the analyses.

Version: 1.0 Page 23 of 48

